### Contraceptivesa allowed during the study include:

---

#### Highly effective methodsb that have low user dependency

Failure rate of <1% per year when used consistently and correctly.

- Implantable progestogen-only hormone contraception associated with inhibition of ovulationb
  - Intrauterine device (IUD)
  - Intrauterine hormone-releasing system (IUS)b
- Bilateral tubal occlusion

---

#### Vasectomized partner

(Vasectomized partner is a highly effective contraceptive method provided that the partner is the sole sexual partner of the WOCBP and the absence of sperm has been confirmed. If not, an additional highly effective method of contraception should be used. Spermatogenesis cycle is approximately 90 days.)

---

#### Highly effective methodsb that are user dependent

Failure rate of <1% per year when used consistently and correctly.

- Combined (estrogen- and progestogen-containing) hormonal contraception associated with inhibition of ovulationc
  - oral
  - intravaginal
  - transdermal
  - injectable
- Progestogen-only hormone contraception associated with inhibition of ovulationc
  - oral
  - injectable

---

#### Sexual abstinence

Sexual abstinence is considered a highly effective method only if defined as refraining from heterosexual intercourse during the entire period of risk associated with the study intervention. The reliability of sexual abstinence needs to be evaluated in relation to the duration of the study and the preferred and usual lifestyle of the participant.)

---

a Contraceptive use by men or women should be consistent with local regulations regarding the use of contraceptive methods for those participating in clinical studies.

b Failure rate of <1% per year when used consistently and correctly. Typical use failure rates differ from those when used consistently and correctly.

c If locally required, in accordance with Clinical Trial Facilitation Group (CTFG) guidelines, acceptable contraceptive methods are limited to those which inhibit ovulation as the primary mode of action.

WOCBP: woman of childbearing potential

## **COLLECTION OF PREGNANCY INFORMATION:**

### **Male participants with partners who become pregnant**

- The Investigator will attempt to collect pregnancy information on any male participant's female partner who becomes pregnant while the male participant is in this study. This applies only to male participants who receive dupilumab.
- After obtaining the necessary signed informed consent from the pregnant female partner directly, the Investigator will record pregnancy information on the appropriate form and submit it to the Sponsor within 24 hours of learning of the partner's pregnancy. The female partner will also be followed to determine the outcome of the pregnancy. Information on the status of the mother and child will be forwarded to the Sponsor. Generally, the follow-up will be no longer than 6 to 8 weeks following the estimated delivery date. Any termination of the pregnancy will be reported regardless of fetal status (presence or absence of anomalies) or indication for the procedure.

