## 7 DISCONTINUATION OF STUDY INTERVENTION AND PARTICIPANT DISCONTINUATION/WITHDRAWAL

### 7.1 DISCONTINUATION OF STUDY INTERVENTION

#### 7.1.1 Definitive discontinuation

In rare instances, it may be necessary for a participant to permanently discontinue study intervention. If study intervention is permanently discontinued, the participant will remain in the study to be evaluated for safety. See the SoA ([Section 1.3](#)) for data to be collected at the time of discontinuation of study intervention.

The participants may withdraw from treatment with the IMP if he or she decides to do so, at any time and irrespective of the reason, or this may be the investigator's decision. All efforts should be made to document the reason(s) for treatment discontinuation and this should be documented in the eCRF.

Participants must be permanently withdrawn from the study treatment for the following reasons:

- At their own request or at the request of their legally authorized representative (legally authorized representative means an individual or judicial or other body authorized under applicable law to consent on behalf of a prospective participant to the patient's participation in the procedure(s) involved in the research).
- If, in the investigator's opinion, continuation in the study would be detrimental to the participant's well-being.
- At the specific request of the Sponsor.
- If they are treated with the specific prohibited medications mentioned in [Section 6.5](#).
- If they miss more than 2 consecutive IMP doses.
- In the event of a protocol deviation, at the discretion of the investigator or the Sponsor.
- Any code broken at the requested of the investigator.
- Pregnancy.
- Anaphylactic reactions or systemic allergic reactions that are related to IMP and require treatment (see [Section 10.8](#)).
- Diagnosis of a malignancy during study, excluding carcinoma in situ of the cervix, or squamous or basal cell carcinoma of the skin.
- Any opportunistic infection or other infections whose nature or course may suggest an immunocompromised status (see [Section 10.9](#)).
- Serum ALT >3 ULN and Total Bilirubin >2 ULN (see [Section 10.6](#)).
- Serum ALT >5 ULN if baseline ALT ≤2 ULN or ALT >8 ULN if baseline ALT >2 ULN (see [Section 10.6](#)).

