### **8.3 ADVERSE EVENTS AND SERIOUS ADVERSE EVENTS**

#### **Adverse event of special interest**

An AESI is an AE (serious or nonserious) of scientific and medical concern specific to the Sponsor's product or program, for which ongoing monitoring and immediate notification by the Investigator to the Sponsor is required. Such events may require further investigation in order to characterize and understand them. Adverse events of special interest may be added, modified or removed during a study by protocol amendment.

For these AESIs, the Sponsor will be informed immediately (ie, within 24 hours), per SAE notification described in [Section 10.3](#), even if not fulfilling a seriousness criterion, using the corresponding pages in the CRF (to be sent) or screens in the eCRF. If an SAE or any AESI of anaphylactic reactions or systemic allergic reactions that are related to IMP and require treatment, or severe injection site reactions lasting longer than 24 hours, occurs in a participant, blood samples should be collected for determination of functional dupilumab concentration, and ADA assessment at or near the onset and completion of the occurrence of the event, if possible.

- Anaphylactic reactions
- Systemic hypersensitivity reactions
- Helminthic infections
- Any severe type of conjunctivitis or blepharitis
- Keratitis
- Clinically symptomatic eosinophilia (or eosinophilia associated with clinical symptoms)
- Pregnancy of a female subject entered in a study as well as pregnancy occurring in a female partner of a male subject entered in a study with IMP/NIMP;
- Pregnancy occurring in a female participant entered in the clinical trial or in a female partner of a male participant entered in the clinical trial. It will be qualified as an SAE only if it fulfills one of the seriousness criteria.

- In the event of pregnancy in a female participant, IMP should be discontinued.
- Follow-up of the pregnancy in a female participant or in a female partner of a male participant is mandatory until the outcome has been determined.
- Abnormal pregnancy outcomes (eg, spontaneous abortion, fetal death, stillbirth, congenital anomalies, ectopic pregnancy) are considered SAEs.
- Significant ALT elevation
  - ALT  $>5$  x ULN in participants with baseline ALT  $\leq 2$  x ULN;  
OR
  - ALT  $>8$  x ULN if baseline ALT  $>2$  x ULN
- Symptomatic overdose (serious or nonserious) with IMP/NIMP

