### **8.3.5 Pregnancy**

- Details of all pregnancies in female participants and female partners of male participants will be collected after the start of study intervention and until the outcome has been determined.

- If a pregnancy is reported, the Investigator should inform the Sponsor within 24 hours of learning of the pregnancy and should follow the procedures outlined in Appendix 4 ([Section 10.4](#)).
- Abnormal pregnancy outcomes (eg, spontaneous abortion, fetal death, stillbirth, congenital anomalies, ectopic pregnancy) are considered SAEs.

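### Appendix 4 limits collection of partner pregnancies to men on dupilumab, which conflicts with Sections 8.3 and 8.3.5 and SAP Table 8 and cannot be applied by a blinded site

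*Protocol*

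**What the plan says.** Protocol Section 10.4 (Appendix 4), under the heading for male participants whose partners become pregnant, first has the investigator attempt to "collect pregnancy information on any male participant's female partner who becomes pregnant" while the man is in the study. The next sentence narrows this: "This applies only to male participants who receive dupilumab". The bullet that follows requires the partner's own consent and submission to the sponsor within 24 hours of learning of the pregnancy.

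Three other places deal with the same event:

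- **Protocol Section 8.3 (AESI list)** counts a pregnancy "in a female partner of a male participant entered in the clinical trial" as an AESI, with immediate notification (within 24 hours). On follow-up it says: "Follow-up of the pregnancy in a female participant or in a female partner of a male participant is mandatory until the outcome has been determined".
- **Protocol Section 8.3.5** states: "Details of all pregnancies in female participants and female partners of male participants will be collected after the start of study intervention". It then directs the investigator to Appendix 4 for the procedure.
- **SAP Table 8** identifies the pregnancy AESI, including partner pregnancy, from the investigator's entry on the Pregnancy eCRF page, for all participants.

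On blinding, the Synopsis says that participants and investigators are masked, and Section 6.3 says that active and placebo syringes look the same.

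**The concern.** The collection rule in Appendix 4 depends on something the site does not know. It also disagrees with the sections that create the duty to report. Because Section 8.3.5 sends the site to Appendix 4 for the procedure, the restricting sentence stands exactly where the investigator will look when a case arises.

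At stake is the completeness of one AESI. A site that tries to honour the restriction has only poor options. It can judge allocation from clinical impression and leave out men it believes to be on placebo, or it can try to learn the allocation. The first would make ascertainment depend on perceived arm, and the second would put the blind at risk for an administrative reason. Protocol Section 9.4.2 presents safety results by treatment group, so differential collection would feed straight into that table.

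**Working it through.** There is no stated figure to reproduce, and no sample size, power or alpha calculation bears on the point. The check sets the texts side by side.

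| Source | Whose partner pregnancies | Limited by arm? |
|---|---|---|
| Protocol Appendix 4, opening sentence | any male participant | no |
| Protocol Appendix 4, next sentence | men receiving dupilumab | **yes** |
| Protocol Section 8.3, AESI list | any male participant in the trial | no |
| Protocol Section 8.3, follow-up | any male participant | no |
| Protocol Section 8.3.5 | all, after start of study intervention | no |
| SAP Table 8 | as ticked on the eCRF | no |

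1. **Is the restriction isolated?** Yes. It is the only one of the six statements that refers to treatment received. The parallel Appendix 4 rule for female participants covers any woman who becomes pregnant while in the study, again without an arm limit.

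2. **Can a site apply it?** No. Investigators are masked and the syringes are indistinguishable. The protocol gives the site no routine access to allocation. Section 6.3 provides a code break for an emergency.

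3. **Can it be read as a filter for use after unblinding?** Not on its wording. It qualifies what the investigator collects, and submission is due within 24 hours of learning of the pregnancy. The decision therefore falls while the trial is blinded.

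4. **How many participants does it touch?** Randomization is 1:1 with about 150 participants, so 150 × 1/2 = 75 are on placebo. That figure includes women and is only a ceiling. If M of the 150 are men, the restriction excludes the partners of about M/2 of them. The documents do not give M, nor an expected number of partner pregnancies, so no expected count of lost cases can be derived.

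**The case against.** The strongest reply is that the sentence will do little harm in practice. Sections 8.3 and 8.3.5 and the opening sentence of the same bullet all point to collecting every case. Because the restriction cannot be applied under blinding, collecting everything is the natural default. AESI notification also has its own route, through the procedure in Section 10.3, which carries no arm limit. SAP Section 4.7 makes the safety analysis descriptive with no testing. The protocol background notes that most studies of this disease report a median age above 50, so few pregnancies are likely. All of this stands, and it is why the point is minor.

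A reader might go further and infer that partner pregnancies will be lost or the blind will be broken. The documents do not support that. No text tells a site to guess allocation, and a site that follows Sections 8.3 and 8.3.5 collects every case and stays blinded.

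A reader might also build a chain from the restriction to a code break and on to permanent withdrawal of study treatment, since Section 7.1.1 lists "Any code broken at the requested of the investigator" among its reasons. But Section 6.3 frames code breaking for emergencies and asks the investigator to make every effort to contact the sponsor beforehand unless that could delay emergency treatment. Appendix 4 does not mention unblinding, and nothing describes a partner pregnancy form as an emergency. The chain needs an investigator to act outside Section 6.3.

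What the reply does not remove is the contradiction. A site with one partner pregnancy finds conflicting instructions on a report due within 24 hours, and one of them cannot be carried out.

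**Conclusion.** The restricting sentence in Appendix 4 is wrong as written. It contradicts the sentence before it, Sections 8.3 and 8.3.5 and SAP Table 8, and a blinded site cannot apply it. The consequence is a risk that this AESI is collected incompletely, or differently by perceived arm, and it arises only if a site acts on the sentence.

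The size cannot be stated beyond the ceiling of about 75 placebo participants of either sex. The effect is confined to ascertainment of one AESI and, less likely, to the blind. Efficacy results, power and type I error are not touched.

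This is best classed as an internal inconsistency of minor severity. A reader might take the sentence for a deliberate choice to leave placebo men out, but the unrestricted wording everywhere else points the other way.

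**What to change.** Delete "This applies only to male participants who receive dupilumab" from Appendix 4 at the next amendment. The appendix then agrees with Sections 8.3 and 8.3.5 and SAP Table 8: partner pregnancies are collected for every male participant regardless of allocation, and nobody needs to be unblinded. SAP Table 8 needs no change.

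If no amendment is near, a short written clarification to sites would protect the data in the meantime.

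The cost is one deleted sentence and at most a few extra partner consent and follow-up forms for men on placebo. It adds no new duty, because Sections 8.3 and 8.3.5 already require these reports.

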### **Female participants who become pregnant**

- The Investigator will collect pregnancy information on any female participant who becomes pregnant while participating in this study. Information will be recorded on the appropriate form and submitted to the Sponsor within 24 hours of learning of a participant's pregnancy. The participant will be followed to determine the outcome of the pregnancy. The Investigator will collect follow-up information on the participant and the neonate and the information will be forwarded to the Sponsor. Generally, follow-up will not be required for longer than 6 to 8 weeks beyond the estimated delivery date. Any termination of pregnancy will be reported, regardless of fetal status (presence or absence of anomalies) or indication for the procedure.
- Any pregnancy complication or elective termination of a pregnancy will be reported as an AE or SAE. A spontaneous abortion is always considered to be an SAE and will be reported as such. Any post-study pregnancy related SAE considered reasonably related to the study intervention by the Investigator will be reported to the Sponsor as described in **Section 8.3.4** of the protocol. While the Investigator is not obligated to actively seek this information in former study participants, he or she may learn of an SAE through spontaneous reporting.
- Any female participant who becomes pregnant while participating in the study will discontinue study intervention.

## **10.5 APPENDIX 5: GENETICS**

[figure not shown]
### **Use/Analysis of DNA and RNA**

- Genetic variation may impact a participant's response to study intervention, susceptibility to, and severity and progression of disease. Variable response to study intervention may be due to genetic determinants that impact drug absorption, distribution, metabolism, and excretion; mechanism of action of the drug; safety, disease etiology; and/or molecular

subtype of the disease being treated. Therefore, where local regulations and IRB/IEC allow, a blood sample will be collected for DNA analysis from consenting participants.

- DNA and RNA samples will be used for research related to dupilumab or PN and related diseases. They may also be used to develop tests/assays including diagnostic tests related to dupilumab or related drugs and atopic/allergic diseases. Genetic research may consist of the analysis of one or more candidate genes or the analysis of genetic markers throughout the genome including whole-exome sequencing, whole-genome sequencing, and DNA copy number variation. Transcriptome sequencing (or other methods for quantitating RNA expression) may also be performed.
- The samples may be analyzed as part of a multi-study assessment of genetic factors involved in the response to dupilumab or study interventions of this class to understand study disease or related conditions.
- The results of genetic analyses will not be reported in the CSR.
- The Sponsor will store the DNA samples in a secure storage space with adequate measures to protect confidentiality.
- The samples will be retained no longer than 15 years or other period as per local requirements.

## 10.6 APPENDIX 6: LIVER AND OTHER SAFETY: SUGGESTED ACTIONS AND FOLLOW-UP ASSESSMENTS

\*If unable to retest in 72 hours, use original lab results to decide on further reporting/monitoring/discontinuation.

[figure not shown]
Note:

“Baseline” refers to ALT sampled at baseline visit; or if baseline value unavailable, to the latest ALT sampled before the baseline visit. The algorithm does not apply to the instances of increase in ALT during screening.

See [Section 10.3](#) for guidance on safety reporting.

[figure not shown]
Normalization is defined as  $\leq$ ULN or baseline value, if baseline value is >ULN.

**INCREASE IN SERUM CREATININE in patients with normal baseline  
(creatininemia between 45 µmol/L and 84 µmol/L)**

Increase in serum creatinine is to be recorded as an AE only if at least 1 of the criteria listed in the general guidelines for reporting AEs in [Section 10.3](#) is met.

[figure not shown]
**INCREASE IN CPK OF NON-CARDIAC ORIGIN AND NOT  
RELATED TO INTENSIVE PHYSICAL ACTIVITY**

Increase in CPK is to be recorded as an AE only if at least 1 of the criteria in the general guidelines for reporting AEs in [Section 10.3](#) is met.

**10.7.2 Investigator's global assessment of prurigo nodularis (IGA PN)**

Copyright @ Center for Chronic Pruritus, University Hospital Münster Under license. For permission to use refer to: [contact]

[figure not shown]
### **10.7.3 Prurigo activity score (PAS)**

[figure not shown]
Copyright @ Center for Chronic Pruritus, University Hospital Münster Under license. For permission to use refer to: [contact]

#### **10.7.4 Dermatology life quality index (DLQI)**

[figure not shown]
©AY Finlay, GK Khan, April 1992, This must not be copied without the permission of the authors.

### 10.7.5 Hospital anxiety and depression scale (HADS)

HADS - United States/English - Version of 30 Jan 17 - Mapi.  
ID058041 / HADS\_AU5\_0\_eng-US.doc

## 10.7.6 EQ-5D-5L

[figure not shown]
© EuroQol Research Foundation. EQ-5D™ is a trade mark of the EuroQol Research Foundation

*Disclaimer: This is a preview of the EQ-5D instrument. It demonstrates the text, questions and response options included in this version. This preview does not represent the final product and should not be used as an official EQ-5D instrument.*

### 10.7.7 Pain numeric rating scale

#### Worst Skin Pain Numerical Rating Scale (Generic)

How would you rate your skin pain at its worst in the past 24 hours?

### 10.7.8 Sleep numeric rating scale

#### Sleep Quality Numerical Rating Scale (Generic)

**Instructions:**

**Please complete the following questions upon awakening for the day.**

Select the number that best describes the quality of your sleep last night.

0	1	2	3	4	5	6	7	8	9	10
Worst possible sleep										Best possible sleep

### 10.7.9 Patient Global Impression of Change of disease (PGIC)

#### Patient Global Impression of Change (PGIC) of PN Disease

Please choose the response below that best describes the overall change in your prurigo nodularis since you started taking the study medication.

- Very much better
- Moderately better
- A little better
- No change
- A little worse
- Moderately worse
- Very much worse

#### **10.7.10 Patient Global Impression of Severity (PGIS)**

##### **Patient Global Impression of Severity (PGIS) of PN Disease**

Please choose the response below that best describes the severity of your prurigo nodularis over the past week.

- None
- Mild
- Moderate
- Severe

## 10.7.11 Missed school/work days

### Patients with Prurigo Nodularis (PN)

#### Missed School/Work days BASELINE Visit

Site Number: \_\_\_\_\_ Patient Study Number: \_\_\_\_\_

Visit Date (dd/mmm/yyyy): \_\_\_\_\_ / \_\_\_\_\_ / \_\_\_\_\_ Time of Completion: \_\_\_\_\_ : \_\_\_\_\_ am/pm

#### Employment status

1. Have you been working?

- Yes – I am working full time ( $\geq 4$  days/week)
- Yes – I am working part time ( $< 4$  days/week)
- No – I am not working (unemployed, retired)

For those working (full time or part time):

2. How many days have you missed from work because of your Prurigo Nodularis in the last 4 weeks prior to the visit today?

*Please do not include time you missed from work for taking part in this research.*

Specify: \_\_\_ Days

#### Student status

1. Have you been in school?

- Yes – I am in school full time ( $\geq 4$  days/week)
- Yes – I am in school part time ( $< 4$  days/week)
- No – I am not in school

For those in school (full time or part time):

2. How many days have you missed from school because of your Prurigo Nodularis in the last 4 weeks prior to the visit today?

*Please do not include time you missed from school for taking part in this research.*

Specify: \_\_\_ Days

#### NOTES:

Please make sure the instructions are read to the patient BEFORE they start the questionnaire.

Assessment periods (i.e., time interval from the date of last assessment through the current date) must be continuous. Leave no gaps. Cumulatively, these periods must cover the entire study duration.

Avoid duplicate reporting. If the patient missed school/work because of his/her PN on the day of

assessment, this day should be recorded only once.

Record only days on which patient's PN prevented him/her to go to school/work. Otherwise, do not record the days on which the patient missed school/work only to participate in study visits.

Print Name (First/Last) of Investigator Completing Assessment Signature Date

R668-XXX-Missed School/work Days Version 1.0 BASELINE; date

Page 1 of 1

